**Appendix 3 Dianeal Low Calcium (2.5 mEq/L) Peritoneal Dialysis Solution Formulations**

Component	Dianeal Low Calcium (2.5 mEq/L) PD Solution Formulation (g/L)		
	1.5% Dextrose	2.5% Dextrose	4.25% Dextrose
Dextrose, hydrous	15.0	25.0	42.5
Sodium chloride	5.38	5.38	5.38
Magnesium chloride hexahydrate	0.051	0.051	0.051
Calcium chloride dihydrate	0.183	0.183	0.183
Sodium lactate	4.48	4.48	4.48
Water for injection	qs to 1000 mL	qs to 1000 mL	qs to 1000 mL
Component	Dianeal Low Calcium (2.5 mEq/L) Ionic Composition (mmol/L)		
Sodium	132		
Calcium	1.25		
Magnesium	0.25		
Chloride	95		
Lactate	40		
pH at 25°C	4.0 - 6.5		

#### Appendix 4 Formulas

The following equations d e f will be used to calculate total Kt/Vurea:

$$\text{Peritoneal } \frac{Kt}{V_{urea}} = \frac{\left( \frac{\text{Dialysate urea } \left( \frac{\text{mmol}}{\text{L}} \right)}{\text{Serum urea } \left( \frac{\text{mmol}}{\text{L}} \right)} \times \text{Total Drainage volume of } 24 - h \text{ (L)} \times 7d \right)}{V_{urea}}$$

$$\text{Renal } \frac{Kt}{V_{urea}} = \frac{\left( \frac{24\text{hr urine urea } \left( \frac{\text{mmol}}{\text{L}} \right)}{\text{Serum urea } \left( \frac{\text{mmol}}{\text{L}} \right)} \times 24 - h \text{ urine (L)} \times 7d \right)}{V_{urea}}$$

Total Kt/Vurea = Peritoneal Kt/Vurea + Renal Kt/Vurea

---

d Szeto C., Wong T., Leung C., et al. Importance of dialysis adequacy in mortality and morbidity of Chinese CAPD patients, 2000. *Kidney International*. 2000; 58: 400-407

e Nolph K.D., Moore H.L., Twardowski Z.J., et al. Cross-sectional Assessment of Weekly Urea and Creatinine Clearances in Patients on Continuous Ambulatory Peritoneal Dialysis, 1992. *Asaio Journal*. 1992.

f Keshaviah P.R., Nolph K.D., Prowant B. et al. Defining Adequacy of CAPD with Urea Kinetics. *Baxter Health Corp., University of Missouri, Columbia, and Dialysis Clinic, Inc, Columbia*.

---

## Appendix 5 Definitions of Adverse Events of Special Interest Terms

Aseptic Peritonitis	Inflammation of the peritoneum lining the abdominal cavity as the result of infectious, autoimmune, or chemical processes.
Encapsulating Peritoneal Sclerosis	A devastating but rare complication of long-term PD. The disease is associated with extensive thickening and fibrosis of the peritoneum resulting in the formation of a fibrous cocoon encapsulating the bowel leading to intestinal obstruction.
Hypovolemia	An abnormal decrease in fluid volume or rapid shift from one compartment of body fluid to another.
Hyperglycemia	An abnormally high level of glucose in the blood.
Hypocalcemia	A low blood calcium level, occurs when the concentration of free calcium ions in the blood falls below 2.1 mmol/L.
Hypokalemia	A low blood potassium level, occurs when the concentration of potassium in the blood falls below 3.5 mmol/L.
Hyponatremia	A low blood sodium level, occurs when the concentration of sodium in the blood falls below 135 mmol/L.
Lactic Acidosis	Acidosis due to the buildup of lactic acid in the body.
Medication Error	Errors in prescribing, dispensing, or administering medication with the result that the patient fails to receive the correct drug or the indicated proper drug dosage.

---

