There are inherent risks to PD therapy. Similar to PD therapies with other dextrose-based solutions, such as Dianeal, there are potential risks associated with the use of the AMIA APD Solution Generation System. AMIA APD Generated Solution is expected to have the same safety profile as Dianeal PD Solution. Important identified risks with Dianeal and other dextrose-based solutions that will be applicable to the AMIA APD Generated Solution include: aseptic peritonitis, hypovolemia, hypokalemia, hyponatremia, encapsulating peritoneal sclerosis, and medication error - administration of incorrect glucose concentration. Important potential risks include lactic acidosis, hyperglycemia, and hypocalcemia.

Overall, the benefits outweigh the potential adverse effects of using AMIA APD Generated Solution in patients with ESRD for which PD therapy is indicated. Therefore, the benefit-risk balance is positive for AMIA APD Generated Solution. Participation of PD patients in this prospective study may support future opportunity of PD patients to benefit from a potential access to this approach to PD treatment.

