### 4.3 Exclusion Criteria

Patient who meets ANY of the following criteria will be excluded from the study:

1. Patient with a history of PD catheter dysfunction within 12 weeks prior to study enrollment, as evaluated by the Investigator.
2. Patient who had episodes of peritonitis or exit site infection within 12 weeks prior to study enrollment.
3. Patient who has signs of impending or current infection including a cloudy dialysis effluent or dialysis white cell count  $> 100/\mu\text{L}$  or  $> 0.1 \times 10^9/\text{L}$  (after a dwell time of at least 2 hours), with  $> 50\%$  polymorphonuclear cells, and/or positive dialysis effluent culture.
4. Patient who has a severe primary immune deficiency or other condition that may mask clinical signs of peritonitis, as evaluated by the Investigator.
5. Patient with a history of repeated non-compliance with PD, therapy (e.g., a substantial number of missed clinic visits, missed treatments or a history of mismanagement of diet or medications), as evaluated by the Investigator.
6. Patient who has acute renal failure with the chance for recovery.
7. Patient who is pre-scheduled for a living donor kidney transplant within the next 6 months.
8. Patient who is not expected to live at least 6 months while maintaining PD treatment.
9. Patient who had major abdominal surgery within 6 months prior to study enrollment.
10. Patient with current abdominal hernia, as evaluated by the Investigator.
11. Patient with advanced liver or pulmonary disease, as evaluated by the Investigator.
12. Positive serology test for Hepatitis B Virus or Hepatitis C Virus infection, or aspartate transaminase or alanine aminotransferase  $> 3 \times$  upper limit of normal at Screening.

13. Patient with diagnosed stage III or IV New York Heart Association (NYHA) heart failure. (Appendix 7)
14. Patient who has an active malignancy.b
15. History of a clinically significant illness and/or clinically significant surgery within the past 14 days preceding the Screening Visit as determined by the Investigator.
16. Patient who is enrolled in another interventional clinical study.

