### 7.2.1 Adverse Event of Special Interest

Adverse events of special interest are listed below. The adverse events within this section represent those that are thought to have an association with the use of the AMIA APD Solution Generation System or in conjunction with performing the peritoneal dialysis procedure.

- Aseptic Peritonitis
- Hypovolemia
- Hypokalemia
- Hyponatremia
- Encapsulating Peritoneal Sclerosis
- Medication Error: administration of incorrect glucose concentration
- Lactic Acidosis

- Hyperglycemia
- Hypocalcemia

The definitions of AESIs are provided in [Appendix 5](#).

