### **8.10 End of Study Visit or Early Termination Procedures**

The End of Study assessments will be performed 5-10 days after the last treatment with the AMIA APD Solution Generation System (i.e., at week 13 for patients who completed the 12 weeks of treatment). If a patient discontinues from the study prematurely, every attempt should be made to perform all procedures and evaluations that are scheduled for the End of Study/ Early Termination Visit. A patient who withdraws from the study after installation and after meeting all the inclusion criteria and none of the exclusion criteria is considered an Early Termination patient. In addition, a patient who withdraws from the study after installation but before confirming that all the inclusion criteria and none of exclusion criteria are met and withdraws due to a device-related issue (e.g., leaking, alarms, etc.), is also considered an Early Termination patient.

The following data will be collected:

1. Collection of AEs/ SAEs.
  2. Adverse events of special interest (Refer to Section [7.2.1](#) for the full list of AESIs).
  3. Physical examination including weight.
  4. Assessment by an Investigator or a designee.
  5. Vital Signs.
- 
- 

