14.2.3 Adverse Events of Special Interest (AESI)

In this study, AESIs are defined as any of the following events:

- Aseptic Peritonitis
 - Hypovolemia
 - Hypokalemia
 - Hyponatremia
 - Encapsulating Peritoneal Sclerosis
 - Medication Error: administration of incorrect glucose concentration
 - Lactic Acidosis
 - Hyperglycemia
-
- 

- Hypocalcemia

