14.2.4 Presentation of Adverse Events

An AE overview summary table will be prepared to include the number of patients reporting an AE, the percentage of patients (%) with an AE, the number of events reported, for the following categories:

1. Any treatment emergent adverse event
2. Treatment-emergent SAEs.
3. Treatment-emergent pre-defined AEs of special interest
4. Treatment-emergent study device-related AEs.
5. Treatment-emergent typical PD-related AEs
6. Treatment-emergent study device-related SAEs
7. Treatment-emergent typical PD-related SAEs
8. Treatment-emergent AEs leading to withdrawal.
9. Treatment-emergent AEs leading to death.

Adverse events will be further tabulated by body system using the MedDRA coded values. The table will display the total number of patients reporting an AE, the percentage of patients (%) with an AE, and the number of events reported by overall, system organ class (SOC), and preferred term. Table summaries will be produced for:

- All treatment-emergent AEs
 - Treatment-emergent AEs leading to withdrawal
 - Treatment-emergent SAEs
 - Treatment-emergent AEs leading to death
 - Treatment-emergent pre-defined AEs of special interest
 - Treatment-emergent pre-defined SAEs of special interest
 - Treatment-emergent AEs by severity
 - Treatment-emergent SAEs by severity
-
- 

- Treatment-emergent AEs by relationship to study product
- Treatment-emergent SAEs by relationship to study product
- Treatment-emergent AEs by relationship to typical PD therapy
- Treatment-emergent SAEs by relationship to typical PD therapy
- Treatment-emergent adverse events in $\geq 5\%$ of patients

Adverse events occurring between informed consent and treatment start (pre-treatment AEs), treatment-emergent adverse events, treatment-emergent SAEs, treatment-emergent adverse events leading to withdrawal, treatment-emergent adverse events related to study device, typical PD therapy, or another Baxter product, and adverse events for patients who died will be listed.

For the SAE listing, the seriousness criteria will also be included in the listing.

If there are less than 5 adverse events in one of the bulleted categories above, then a listing may be created instead of a table for those AEs.

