17. LIST OF TABLES, FIGURES AND LISTINGS

Table Number	Table Name
14.1.1	Patient Overview
14.1.2	Patient Disposition
14.1.3	Protocol Deviations Summary
14.1.4	Categorical Demographic and Baseline Characteristics
14.1.5	Continuous Demographic and Baseline Characteristics
14.2.1	Overall Testing of the Chemical Composition of the Dialysis Solution (Primary Efficacy Endpoint)
14.2.2	Individual Parameter Testing of the Chemical Composition of the Dialysis Solution
14.2.3	Individual Parameter Summary of the Chemical Composition of the Dialysis Solution
14.2.4	Total Kt/V _{urea} Summary (Secondary Efficacy Endpoint)
14.2.5.1	eDiary Treatment Summary
14.2.5.2	Treatment Interruptions Summary
14.3.1.1.1	Summary of Adverse Events
14.3.1.1.2	Treatment-Emergent Adverse Events by SOC and Preferred Term
14.3.1.1.3	Serious Treatment-Emergent Adverse Events by SOC and Preferred Term
14.3.1.1.4	Treatment-Emergent Adverse Events Related to Study Device by SOC and Preferred Term
14.3.1.1.5	Treatment-Emergent Adverse Events Related to Typical PD Therapy by SOC and Preferred Term
14.3.1.1.6	Treatment Emergent Adverse Events Related to Another Baxter Product by SOC and Preferred Term
14.3.1.1.7	Serious Treatment-Emergent Adverse Events Related to Study Device by SOC and Preferred Term
14.3.1.1.8	Serious Treatment-Emergent Adverse Events Related to Typical PD Therapy by SOC and Preferred Term
14.3.1.1.9	Serious Treatment-Emergent Adverse Events Related to Another Baxter Product by SOC and Preferred Term
14.3.1.1.10	Treatment-Emergent Adverse Events Leading to Withdrawal by SOC and Preferred Term
14.3.1.1.11	Treatment-Emergent Adverse Events Leading to Death by SOC and Preferred Term

14.3.1.1.12	Treatment-Emergent Adverse Events of Special Interest by SOC and Preferred Term
14.3.1.1.13	Treatment-Emergent Adverse Events in $\geq 5\%$ of Patients by SOC and Preferred Term
14.3.1.3.1	Treatment-Emergent Adverse Events by SOC, Preferred Term, and Severity
14.3.1.3.2	Treatment-Emergent Adverse Events by SOC, Preferred Term, and Relationship with Study Device
14.3.1.3.3	Treatment-Emergent Adverse Events by SOC, Preferred Term, and Relationship with Typical PD Therapy
14.3.1.3.4	Treatment-Emergent Adverse Events by SOC, Preferred Term, and Relationship with Another Baxter Product
14.3.4.1	Hematology Laboratory Summary at Baseline
14.3.4.2	Chemistry Laboratory Summary at Baseline
14.3.5.1	Vital Signs Summary and Change from Baseline
14.3.6.1	Summary of Device Deficiencies

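### Protocol Appendix 5 defines the special-interest event aseptic peritonitis so that it includes infectious causes, contradicting its own label and leaving the special-interest count open to two readings

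*Protocol*

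**What the plan says.** Protocol section 7.2.1 lists nine AESIs. Aseptic peritonitis is the first and the only peritonitis term. The section then points to Appendix 5: "The definitions of AESIs are provided in" that appendix. The Appendix 5 entry for aseptic peritonitis reads "Inflammation of the peritoneum lining the abdominal cavity as the result of infectious, autoimmune, or chemical processes".

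Protocol section 1.2 uses the same label for a risk of the solution: "Important identified risks with Dianeal and other dextrose-based solutions that will be applicable to the AMIA APD Generated Solution include: aseptic peritonitis".

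SAP section 14.2.3 opens with "In this study, AESIs are defined as any of the following events" and repeats the nine names. It gives no definitions, no Preferred Terms and no reference to Appendix 5. SAP section 12 records no change from the protocol's planned analyses.

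AESI membership feeds these outputs:
- item 3 of the adverse event overview in SAP section 14.2.4;
- the AESI and serious-AESI summaries promised in the same section;
- Table 14.3.1.1.12 in SAP section 17, "Treatment-Emergent Adverse Events of Special Interest by SOC and Preferred Term";
- Listing 16.2.7.1.8.

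**The concern.** Aseptic means without infection, so a definition that starts with infectious processes contradicts the term it defines. Two people working correctly from different parts of these documents would classify a bacterial peritonitis differently, one as an AESI and the other not.

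At stake is a pre-defined safety count in a study whose results are entirely descriptive. If the reading is chosen after the cases are known, the choice is discretionary. Sites need a single meaning as well: protocol section 8.10 has AESIs collected at the End of Study visit, and Table 5 in section 7.1 says that such events may call for rapid communication to the sponsor.

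**Working it through.** The plan states no figure on this point, so there is none to reproduce. The check is a comparison of texts, followed by simple arithmetic on the size of the shift.

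**1. Is Appendix 5 operative?** Yes. Section 7.2.1 names it as the source of the AESI definitions. Other entries in it are working case definitions with cut-offs in mmol/L: calcium below 2.1, potassium below 3.5 and sodium below 135.

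**2. The two readings of an infectious peritonitis**

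| Text followed | Is it an AESI? |
|---|---|
| Label in protocol 1.2, protocol 7.2.1 and SAP 14.2.3 | No |
| Definition in protocol Appendix 5 | Yes |

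Exclusion criterion 2 uses the unqualified word: "Patient who had episodes of peritonitis or exit site infection within 12 weeks prior to study enrollment". This suggests that the protocol drops the qualifier when it means any peritonitis. It is weak evidence, because the criterion does not contrast the two terms.

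**3. Does the SAP settle it?** No. A list of names cannot decide between a name and its definition. The documents also do not say whether AESI status is entered by the site or derived in programming. In the first case the sites' reading fixes the data; in the second the programmer's reading fixes the count.

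**4. Size per patient.** Let N be the Safety Set and k the number of patients with infectious peritonitis and no other AESI. The shift in the AESI percentage between the readings is 100 × k / N. The documents give a target of 30 completers and a ceiling of 50 enrolled, so N = 30 and N = 50 are used as illustrative ends.

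| k (assumed) | N = 50 | N = 30 |
|---|---|---|
| 1 | 1/50 = 2.0 points | 1/30 = 3.3 points |
| 3 | 3/50 = 6.0 points | 3/30 = 10.0 points |

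The Safety Set also includes treated patients who do not complete. If the target of 30 completers is met, the N = 30 column is therefore an upper bound for each k. The values of k are assumptions, since the documents give no peritonitis rate.

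**5. Format.** SAP section 14.2.4 adds a small-count rule: "If there are less than 5 adverse events in one of the bulleted categories above, then a listing may be created instead". The reading could decide whether the AESI category falls under that limit. The rule is optional and covers only the bulleted categories, so the overview row keeps its count and percentage either way.

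**The case against.** The strongest reply is that this is one misplaced line. The SAP governs the tables and fixes the AESI set by name, the protocol's risk section uses the same name, and the Appendix 5 entry looks like a general definition of peritonitis set under the wrong heading. Most analysts would follow the label. The case report form and the Safety Management Plan, which are not among these documents, may already settle the matter.

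Much of that stands. The label is probably what was meant, and the consequences are narrow. But the protocol makes the misplaced line the stated definition, and nothing in the SAP overrides it. If it is a slip, it should be corrected before lock.

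A reader might infer three stronger points that the documents do not support.

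- **Peritonitis cases could go unreported.** They would not. SAP section 14.2.4 tabulates all treatment-emergent events, and the serious ones, by system organ class and Preferred Term, and the events are listed. A case admitted through Appendix 5 would appear in the AESI table under its own Preferred Term.
- **The safety endpoints are compromised.** The primary safety endpoints are water tests. The secondary safety endpoint names adverse events, device effects, alarms and vital signs, not AESIs. No decision rule uses the AESI count.
- **The plan is wrong to lack a combined peritonitis count, or an AESI for peritonitis of any cause.** Neither document promises one. Wanting to set such a count beside the water results is a reasonable preference, but its absence is not an error.

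**Conclusion.** The contradiction is real and limited to AESI membership. An operative case definition in Appendix 5 conflicts with the term used in protocol sections 1.2 and 7.2.1 and SAP section 14.2.3, and the SAP does not resolve it. The AESI overview row, the AESI summaries and Listing 16.2.7.1.8 can therefore include or omit infectious peritonitis depending on which text is applied.

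The size is 2.0 to 3.3 percentage points for each affected patient with no other AESI, for a Safety Set between 50 and 30. The total cannot be calculated from the documents. The correction should be made because it is specific and cheap, not because any main conclusion of the study depends on it.

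**What to change.** Correct the Appendix 5 entry so that aseptic peritonitis means peritoneal inflammation from non-infectious causes, for example autoimmune or chemical.

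If the protocol is not amended, state that definition in SAP section 14.2.3 with the Preferred Terms that qualify, before database lock, and replace the no-change statement in SAP section 12 with a record of it. The list should say whether a term that gives no cause qualifies, because effluent cell count and culture are scheduled only at Screening.

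The SAP route costs one sentence, a short term list and an entry in section 12; the events are already collected as adverse events. The protocol route also needs an amendment and, under protocol section 11.2, approval by the Institutional Review Board. If sites enter AESI status themselves, entries made under the Appendix 5 wording would need to be checked against the corrected definition.

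Optionally, a descriptive row outside the AESI set could count patients with peritonitis of any cause, each once. That is a preference and not part of the correction.

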## **6.5 Clinical Laboratory Tests**

### **6.5.1 Laboratory Parameters**

Laboratory assessments will occur at Screening and after the patient has been dialyzing for at least 4 weeks (occurring one time during Week 5, 6, 7 or 8 of the Study Treatment Period), as outlined in [Appendix 2](#). If a patient misses 4 consecutive days of prescribed therapy with AMIA APD Solution Generation System then the total Kt/Vurea assessment (between Weeks 5-8) should be deferred by 1 week to allow a full week of prescribed treatment using the AMIA APD Solution Generation System.

---

Should a medical emergency arise, a local laboratory may be utilized; however, a copy of the laboratory certification, laboratory normal ranges and methodologies will be required. A list of laboratory tests is provided in [Table 4](#).

Because of the potential for false-positive beta serum human chorionic gonadotropin ( $\beta$ -hCG) test results in females with chronic kidney disease and end stage renal disease, both qualitative and quantitative serum pregnancy tests should be taken.

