**Table 4. List of Laboratory Testsa**

Blood	Peritoneal	Urine
$\beta$ -hCG Hepatitis B and Hepatitis C b CBC with differential Chemistry Profile c	PD effluent: WCC with differential Cell culture  24-hour PD effluent: d Total Volume Creatinine Urea nitrogen	24-hour urine collection d Total volume Creatinine Urea nitrogen

$\beta$ -hCG = beta serum human chorionic gonadotropin; CBC = complete blood count; PD = peritoneal dialysis; WCC = white cell count

a At Screening, chemistry, serology, and hematology tests are completed at a central laboratory. At other time points, they are completed at a local laboratory.

b Patients will be screened (those without a history of positive Hepatitis B or Hepatitis C serology) for both infections at the Screening Visit.

-Hepatitis B: Hepatitis B surface antigen (HBsAg) in acute and chronic infection;

-Hepatitis C: Screening assay (EIA or CIA) for anti-Hepatitis C virus (HCV).

If positive, automatic verification of positive Screening results by an additional, more specific assay (e.g., nucleic acid testing [NAT] for HCV RNA) will be done.

c The chemistry profile includes glucose, calcium, albumin, total protein, sodium, potassium, bicarbonate, chloride, creatinine, blood urea nitrogen, alkaline phosphatase, alanine aminotransferase, aspartate amino transferase, bilirubin, and phosphorus.

d 24-hour urine (if not anuric) and 24-hour peritoneal effluent collection for total Kt/Vurea will occur one time during Week 5, 6, 7 or 8 of the Study Treatment Period.

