### **6.5.6 Sample Collection, Storage, and Shipping**

A study specific Laboratory Manual will be provided from each of the central laboratories to the PI and will include detailed instructions on the collection, preparation, storage, and shipping procedures for study samples and the appropriate laboratory ranges. Collection of 24-hour PD effluent samples will be made using the batch method. All laboratory samples will be collected, stored, shipped and processed by the laboratories according to each central lab's procedures.

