**Appendix 2 Schedule of Clinical Laboratory Evaluations**

Observation	Screening	Total Kt/Vurea Visit
Blood Draw:		
Serum $\beta$ -hCG a	X	
Hepatitis B b	X	
Hepatitis C b	X	
CBC with differential	X	
Chemistry Profile c	X	
Creatinine d		X
Urea Nitrogen d		X
PD Effluent:		
White Cell Count with differential	X	
Cell Culture	X	
Total Kt/V urea d	X	X
24-hour PD Effluent Collection:		
Total Volume	X	X
Creatinine	X	X
Urea Nitrogen	X	X
24-hour Urine Collection:		
Total Volume	X	X
Creatinine	X	X

---

Observation	Screening	Total Kt/V urea Visit
Urea Nitrogen	X	X

a Women of childbearing potential (not menopausal or surgically sterile) must have a negative serum pregnancy test result within 14 days prior to initiation of study product.

-If qualitative serum  $\beta$ -hCG results are positive, repeat quantitative serum pregnancy test within 48 hours.

-If quantitative serum  $\beta$ -hCG levels show clinically significant rise, within 48 hours, serum progesterone level should be taken. Serum progesterone > 5 ng/mL will exclude a patient from the study.

b Patients will be screened (those without a history of positive Hepatitis B or Hepatitis C serology) for both infections at the Screening Visit.

-Hepatitis B: Hepatitis B surface antigen (HBsAg) in acute and chronic infection;

-Hepatitis C: Screening assay (EIA or CIA) for anti-Hepatitis C virus (HCV). Automatic verification of positive Screening results by an additional, more specific assay (e.g., nucleic acid testing [NAT] for HCV RNA).

c The chemistry profile includes glucose, calcium, albumin, total protein, sodium, potassium, bicarbonate, chloride, creatinine, blood urea nitrogen, alkaline phosphatase, alanine aminotransferase, aspartate amino transferase, bilirubin, and phosphorous.

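### Four AESIs are defined by a blood level and a fifth would need a blood test, but none has that test scheduled on treatment; the aseptic peritonitis definition and one SAP baseline rule also need correcting

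*Protocol*

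**What the plan says.** Protocol 7.2.1 and SAP 14.2.3 list the same nine AESIs, and Protocol Appendix 5 defines them. Hyponatremia is "A low blood sodium level, occurs when the concentration of sodium in the blood falls below 135 mmol/L". Hypokalemia is "A low blood potassium level, occurs when the concentration of potassium in the blood falls below 3.5 mmol/L". Hypocalcemia is "A low blood calcium level, occurs when the concentration of free calcium ions in the blood falls below 2.1 mmol/L". Hyperglycemia is a raised blood glucose with no limit given. Lactic acidosis is described by its mechanism, with no test or limit. Aseptic peritonitis is "Inflammation of the peritoneum lining the abdominal cavity as the result of infectious, autoimmune, or chemical processes".

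In Protocol Appendix 2 the row "Chemistry Profile" is marked at Screening only. At the Total Kt/V visit (once in Weeks 5 to 8) the blood tests marked are creatinine and urea nitrogen. Protocol 6.9 leaves other testing to local standard of care. Under Protocol 7.2 a laboratory abnormality becomes an AE if it needs intervention, leads to discontinuation, or is judged clinically significant by the Investigator.

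SAP 14.2.4 tabulates treatment-emergent AESIs by number of patients, percentage and number of events. SAP 16.3 keeps unscheduled-visit results out of the tables. SAP 14.3.4 uses Screening as the laboratory baseline, except for blood creatinine and urea nitrogen, whose baseline is to come from the Baseline Period.

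**The concern.** Protocol 1.2 names hypokalemia and hyponatremia as important identified risks, and lactic acidosis, hyperglycemia and hypocalcemia as important potential risks. It also expects the generated solution to share the safety profile of Dianeal. A reader of the final report could take a low or zero AESI count as support for that expectation. If nobody is scheduled to have the relevant blood test after Screening, the count also depends on how often each site happened to test, and the tables do not show that.

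The two smaller items are of a different kind, because a stated rule points the analysis the wrong way. A definition of an aseptic condition that admits infectious causes lets one AESI row mix two different events. A baseline taken from a period with no blood draw for those tests leaves the change from baseline without a starting value.

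**Working it through.** The plan gives no figure to reproduce: it is descriptive and Protocol 10.2 reports no sample-size calculation. The check sets the AESI definitions against the laboratory schedule.

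**1. Definitions against scheduled tests** (Protocol 7.2.1, Appendix 5, Appendix 2 with its footnote c)

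| AESI | Defined by a blood level? | Test in the chemistry profile? | Scheduled on treatment? |
|---|---|---|---|
| Hyponatremia | Yes, sodium below 135 mmol/L | Yes | No |
| Hypokalemia | Yes, potassium below 3.5 mmol/L | Yes | No |
| Hypocalcemia | Yes, free calcium below 2.1 mmol/L | Calcium listed, not specified as free | No |
| Hyperglycemia | Yes, no limit | Yes (glucose) | No |
| Lactic acidosis | No test named; blood test needed in practice | Bicarbonate only, no lactate | No |
| The other four | No | Not applicable | Not applicable |

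Defined by a blood level: 4 of 9. Needing a blood test in practice: 4 + 1 = 5 of 9. Of those 5, with the test scheduled on treatment: 0.

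**2. Analytes.** The profile has 15 analytes. Two of them (creatinine, urea nitrogen) are measured again at the Total Kt/V visit, so 15 − 2 = 13 are scheduled at Screening only.

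**3. What a zero would mean.** The AESI percentage is patients with the event divided by patients in the Safety Set. With an assumed 30 patients and no events it prints 0/30 = 0.0%, whether all 30 or none had the test on treatment. Local values from unscheduled visits go to listings (SAP 16.3), so no table gives the number tested.

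**4. What one added panel would give.** Of the 5 AESIs, 2 (sodium, potassium) could be counted against a numeric limit. Glucose could only be summarised, calcium must wait until its definition is settled, and lactate would remain unmeasured. If none of n patients tested is below a limit, the one-sided 95% upper limit is 1 − 0.05^(1/n):
- n = 30: 1 − 0.05^(1/30) = 1 − 0.905 = 9.5%
- n = 50: 1 − 0.05^(1/50) = 1 − 0.942 = 5.8%

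This bounds prevalence at that one draw and assumes every patient is tested. At present n is unknown, so no such limit can be stated.

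**5. Baseline for blood creatinine and urea nitrogen.** Protocol 8.4 lists no blood test in the Baseline Period. Appendix 1 marks laboratory evaluations at Screening and the Total Kt/V visit only. A serum pregnancy test may fall in the Baseline Period (inclusion criterion 11), but it supplies neither analyte. Both are in the Screening profile. Read literally, the SAP 14.3.4 rule therefore finds no scheduled baseline value for any patient.

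**6. Aseptic peritonitis.** The term excludes infection and its definition includes it. A case of infectious peritonitis meets the definition as worded and could enter that AESI row (1 of 9).

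**The case against.** The strongest reply is that AESIs here serve monitoring and rapid communication and are not endpoints or incidence estimates. AEs are solicited actively and collected on every treatment day. The Investigator assesses patients weekly and the medical monitor reviews laboratory data. The solution is tested at four simulated treatments and its conductivity is checked after each heater-bag replenish. Crossing an Appendix 5 limit does not by itself make an AE under Protocol 7.2, and one extra draw cannot give a 12-week incidence. SAP 16.1 lets Screening data stand in for a missing baseline, Kt/V has its own baseline rule, and preferred-term tables would show infectious peritonitis reported as such.

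Most of this stands, and it keeps the point modest. It does not supply a scheduled serum value: the stated minimum for the weekly assessment includes no blood test, and potassium is not a listed component of the solution. The SAP 16.1 fallback is only permissive.

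A reader might also infer four stronger things that the documents do not support:
- **That these events would be missed or lost from the tables.** SAP 16.3 restricts laboratory values, not AE reports; a reported event still reaches the AESI tables.
- **That AESI rates would be diluted by whole-Safety-Set patient-years.** The rate in SAP 14.2.1 applies unless otherwise specified, and SAP 14.2.4 lists patients, percentage and events for the AESI table, with no rate. Such a rate may not be a planned output.
- **That Table 4 footnote a proves a panel was left off the schedule.** It says of chemistry, serology and hematology: "At other time points, they are completed at a local laboratory". For chemistry, the creatinine and urea nitrogen at the Total Kt/V visit can satisfy that.
- **That five definitions are worded as blood levels.** Four are; lactic acidosis is added on practical grounds.

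**Conclusion.** The point holds, with minor to moderate weight. None of the five AESIs that depend on a blood result has that result scheduled on treatment. Their counts will rest on opportunistic testing with no known number tested, which limits how a zero may be read. It does not make the events undetectable.

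Two statements are wrong as written: the SAP 14.3.4 baseline for blood creatinine and urea nitrogen, and the Appendix 5 definition of aseptic peritonitis. The baseline error is small, given the SAP 16.1 fallback and the separate Kt/V rule. Adding the panel is an improvement to the design, not the repair of a contradiction.

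The conclusion rests on reading Appendix 2 as the full laboratory schedule and on lactic acidosis needing a blood test in practice. The 9.5% and 5.8% limits assume that all 30 or all 50 patients are tested with none below the limit. They are not AESI incidences.

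**What to change.** 1. **SAP 14.3.4 (correction).** Make Screening the baseline for blood creatinine and urea nitrogen. Cost: SAP wording.

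2. **Protocol Appendix 5 (correction).** Reconcile the term aseptic with the infectious causes in its definition, and report aseptic and infectious peritonitis separately by the Investigator's recorded diagnosis. Cost: protocol wording. The existing preferred-term tables can carry the split, so no new table is needed.

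3. **Total Kt/V visit (improvement).** Add the existing chemistry profile to the blood draw already planned. In one SAP table report:
   - the number tested;
   - the change from Screening;
   - counts below the Appendix 5 sodium and potassium limits, split by Screening status because the entry criteria do not exclude low values.

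   Label these as one-time laboratory findings, separate from AESI incidence. Do not count calcium until free calcium in Appendix 5 is reconciled with calcium in the profile, and state that lactate is not measured. Name the laboratory: if Table 4 footnote a is followed, change from Screening also contains a change from central to local laboratory.

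   Cost: one panel per patient, one table, and an amendment with IRB approval (Protocol 11.2). It reaches only patients not yet past that visit, a number the documents do not give. They also do not say whether the planned sample volume is enough for the full profile.

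4. **If no amendment is made.** Make the SAP change in item 1, report the peritonitis split, and state in the report that these five AESIs were found opportunistically with no known number tested. Cost: a sentence.
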